#### **Tertiary/Exploratory Efficacy Endpoints**

- MCCB composite score – a common efficacy endpoint in trials of drugs for cognition enhancement in schizophrenia and schizoaffective disorder, providing evidence of global cognitive improvement.
- MCCB individual subscales and supplementary cognitive tests – these subscales and tests will provide additional information regarding the efficacy of MMFS for improving specific cognitive domains in patients with schizophrenia or schizoaffective disorder. We believe that MMFS may improve other aspects of cognition in addition to working memory, especially those that involve frontal cortex function.
- A working memory composite score derived from the two MCCB working memory subscale tests along with the Brown-Peterson's Auditory Consonant Trigrams test. Deriving a composite score from 3 working memory tests may be superior to the MCCB working memory subscale, which is a composite comprised of only 2 working memory tests. This possibility will be tested to identify the best composite measure of working memory for future trials.
- Responder analysis – the number of subjects achieving a clinical significance cutoff of improving at least one half of a standard deviation (T-score change  $\geq 5$ ) on the working memory subscale of the MCCB, to evaluate the clinical significance of any MMFS treatment effects; an analogous approach will be employed for secondary outcomes.
- Positive and negative symptoms – Positive symptoms will be assessed with the PANSS positive

scale, and negative symptoms will be assessed with the PANSS negative scale and the BNSS. We hypothesize that MMFS-202-302 may significantly improve negative and positive symptoms, at least partially independently from its cognition enhancing effects.

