## 6.0 STUDY PROCEDURES

Study visits will include screening and 5 treatment visits (baseline, Weeks 1, 3, 6, and 9). Patients will be contacted by telephone at Weeks 2, 4, 5, 7, and 8 for monitoring of medication compliance, change in concomitant medication, and adverse events. Please see Appendix 1 – Schedule of Assessments.

At screening, the Structured Clinical Interview for Diagnosis for DSM Disorders (SCID) will be completed for confirmation of psychiatric diagnosis. A medical/psychiatric history will also be collected and a physical exam will be performed. Vital signs including weight, height, waist and hip measurement will be obtained at screening to record body mass index.

Subjects will be administered MMFS-202-302 at a fixed single dose of 2 grams (1 gram twice per day),

or placebo after the completion of the baseline assessments.

Methods:

- A) Measurement and Treatment Research to Improve Cognition in Schizophrenia (MATRICS) battery, including some supplemental cognitive assessments (FAS, ACT, WCST)
- B) Positive and Negative Syndrome Scale (PANSS) for schizophrenia and schizoaffective disorder
- C) MRI assessments:
  - a. Structure: MPRAGE (T1), T2
  - b. Function: Resting connectivity
  - c. Function: Reward/aversion and attention: fMRI paradigm of IAPS (standardized images selected to be neutral, pleasurable, or arousing) and Spinner Task
  - d. Function: Capacity working memory task
- D) A set of cognitive psychological paradigms performed outside of the magnet following the MRI scan:
  - a. Keypress task for an adaptation of the International Affective Picture Set (IAPS)
  - b. A spinner wheel rating task of the reward/aversion associated with monetary gains/losses
- E) Brief Negative Symptom Scale (BNSS)
- F) Calgary Depression Scale for Schizophrenia
- G) Clinical Global Impression of Severity (CGI-S) and Change (CGI-C)
- H) Measurement of RBC Mg at baseline and end of study
- I) EEG evaluation, measuring connectivity and activation using learning and memory tests

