## 8.0 STATISTICAL CONSIDERATIONS

### 8.1 Analysis of Clinical Data

Data will first be analyzed for efficacy on a per-protocol basis. The per-protocol population will include all subjects who complete all scheduled visits (+/- 5 days from planned visit time), have no protocol deviations that in the judgment of the principal investigator would invalidate their efficacy data, and achieve medication compliance of 80-120% (determined by pill counting; if pill packs are not available for confirmation, self-report of compliance will be used). Participants whose assessment falls +10 days or less from the scheduled visit will be included in per-protocol population, only if they were taking the study compound throughout. Data will secondarily be analyzed for efficacy on an intent-to-treat basis, with last observation carried forward (LOCF) for missing values or dropouts; subjects who did not receive any study compound will be excluded from the full analysis set, preserving the intent-to-treat principle. The primary analysis will be a univariate ANCOVA adjusting for baseline differences in the dependent measures of interest. We would also examine some variables categorically. The MATRICS working memory subscale T-score at 9 weeks will be the primary endpoint. Secondary endpoints will include the Clinical Global Impression of Change (CGI-C); the MCCB composite score; other individual cognitive domain subscale T-scores of the MCCB; a working memory composite score comprised of the 2 MCCB working memory subscale tests and the ACT test; and the PANSS positive and negative scales and BNSS. All endpoints will be evaluated as 9-weeks change from baseline, except for PANSS, which will be evaluated at both 6 and 9 weeks compared to baseline. Responder analyses will also be carried out using a chi-square test for the MCCB working memory subscale as a secondary endpoint evaluating clinical significance, using a cutoff of 0.5 standard deviation improvement (T-score improvement of  $\geq$  5 points). Finally, separate exploratory subgroup analyses will be performed on the MCCB working memory subscale T-score restricted to the subset of subjects who score 0, 0.5, or 1.0 SD or below the mean for normal age-matched normative data for that subscale. Analogous subgroup analyses will also be performed for the MCCB composite score, and the other MCCB subscale scores.

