Alpha will be set at 0.05 for all analyses. The individual scores for each of the 6 other neuropsychological MCB subscales, and supplementary cognitive tests (ACT, WCST, FAS), as well as the CGI-C measure of functional change will be evaluated to provide supporting information for primary and secondary measures.

Assumptions for the power analysis included random assignment into one group receiving placebo and one MMFS-202-302. The MCB, as the primary instrument will be collected at baseline and at end point (9 weeks). Using univariate ANCOVA with baseline score as covariate, the time average difference in the response variable will be compared between groups to detect treatment difference. Based on Javitt et al, 2012, we assume the mean baseline working memory score will be 36.4, SD 11.7 for both groups. We assume the placebo group will show no improvement with an SD of change of 6.5, while the treatment group will improve a mean of 5 points with the same SD of change, a medium effect. We assume the correlation coefficient of repeated observation to be 0.5 and the covariance structure to be compound symmetry. The power calculation was conducted with alpha level of 0.05. Full results are available upon request. With a two-sided test, the analysis reveals that 28 subjects per group are required assuming 5 points of improvement of the treatment group compared to the placebo for the desired power of 80% with alpha level of 0.05. We plan to recruit 30 per group to account for drop outs. Thus, allowing for attrition up to 20%, this sample size will provide 74-83% power to detect the hypothesized medium treatment effect.

We will assess MMFS-202-302 effects on negative and positive symptoms as additional endpoints, as measured by the BNSS and PANSS. Further, we will analyze the effect on drug tolerability as determined by the following: body weight, body mass index (BMI), waist circumference, and movement rating scales.

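### The primary ANCOVA could also adjust for the baseline Auditory Consonant Trigrams score already collected: an optional precision gain, nil to modest, not the correction of an error

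*Combined protocol and SAP*

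**What the plan says.** **Model.** Section 8.1 says: "The primary analysis will be a univariate ANCOVA adjusting for baseline differences in the dependent measures of interest". The power paragraph in the same section describes the same single-covariate model: "Using univariate ANCOVA with baseline score as covariate".

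**Endpoint.** "The MATRICS working memory subscale T-score at 9 weeks will be the primary endpoint". Section 3.0 explains that this subscale is built from two tests.

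**ACT.** Section 6.0 lists the MATRICS battery as "including some supplemental cognitive assessments (FAS, ACT, WCST"). Section 5.1 says that the site gives these supplementary tests to all its research patients and that randomisation follows the baseline assessments. Appendix 1 schedules the extended battery on Day 1 and at the end of the study. Section 6.0 places the first dose after the baseline assessments. Baseline ACT is therefore a pre-treatment measurement.

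**What the plan does with ACT.** It appears as a supporting test and as one part of a three-test working memory composite, which section 3.0 lists as tertiary/exploratory and section 8.1 as secondary. On that composite, section 3.0 says: "Deriving a composite score from 3 working memory tests may be superior to the MCCB working memory subscale", and adds: "This possibility will be tested to identify the best composite measure of working memory for future trials". ACT is nowhere named as a covariate for the primary endpoint.

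**The concern.** A baseline score made from two tests measures working memory with some error. A second baseline measure of the same domain can explain part of the week-9 variance that this error leaves unexplained. If it does, the treatment difference is estimated more precisely with no extra testing of patients. Because ACT is measured before randomisation, adjusting for it in a prespecified model introduces no bias.

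The trial plans 30 patients per arm, and section 8.1 gives 74% power at the lower end of its range, below its own 80% target. A few points of power would be useful here.

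**Working it through.** **Inputs from section 8.1.** Difference 5 points; SD of change 6.5; baseline SD 11.7; correlation of repeated observations 0.5; two-sided alpha 0.05; power 80%; 30 per arm; attrition up to 20%, which leaves 24 per arm.

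**Step 1: the plan's own figure.** This compares mean change between two groups, with a noncentral t on 2n - 2 degrees of freedom and noncentrality 5 / (6.5 × √(2/n)).
- The smallest n with 80% power is 28 per arm (80.7%), as stated: "With a two-sided test, the analysis reveals that 28 subjects per group are required".
- Power is 83.4% at 30 per arm and 74.2% at 24 per arm, matching the stated 74-83%.

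**Step 2: residual SD with one covariate.** The residual SD is 11.7 × √(1 - r²), where r is the correlation between the baseline and week-9 subscale. The documents support two values of r:
- r = 0.5, as stated. Residual SD = 11.7 × √0.75 = 10.13, and power at 30 per arm is 46.8%.
- r = 1 - 6.5² / (2 × 11.7²) = 0.846, implied by the two SDs. Residual SD = 11.7 × √(1 - 0.846²) = 6.24, and power at 30 per arm is 86.2%.

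These two values conflict, which is a separate matter. Both are carried forward here.

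**Step 3: what a second covariate does.** Let a be the correlation of baseline ACT with the baseline subscale, and b its correlation with the week-9 subscale. The partial correlation is

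p = (b - r·a) / √((1 - r²)(1 - a²)),

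and residual variance is multiplied by 1 - p². One more degree of freedom is used (2n - 4 in place of 2n - 3). The documents give neither a nor b.

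**Step 4: assumed range.** None of these assumptions comes from the documents. ACT reliability q is 0.4 to 0.8, nine-week trait stability s is 0.9 to 1.0, and the correlation t between the traits behind ACT and the subscale is 0.8 to 1.0, with independent errors. Subscale reliability is r/s, a = t × √(q·r/s) and b = s·a.

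| r | t | p | Fall in residual variance | Residual SD | Power, 30 per arm |
|---|---|---|---|---|---|
| 0.85 | none (one covariate) | – | – | 6.24 | 86.2% |
| 0.85 | 0.8 | 0.06 to 0.25 | 0.3% to 6.4% | 6.23 to 6.04 | 86.3% to 88.3% |
| 0.85 | 1.0 | 0.08 to 0.42 | 0.6% to 17.5% | 6.22 to 5.67 | 86.4% to 91.9% |
| 0.5 | none (one covariate) | – | – | 10.13 | 46.8% |
| 0.5 | 0.8 | 0.19 to 0.34 | 3.5% to 11.5% | 9.95 to 9.53 | 48.1% to 51.5% |
| 0.5 | 1.0 | 0.25 to 0.47 | 6.1% to 22.2% | 9.82 to 8.94 | 49.1% to 56.7% |

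In each row the low end has q = 0.4 and s = 0.9, and the high end has q = 0.8 and s = 1.0. As an example, take r = 0.5, t = 1, s = 1, q = 0.8. Then a = b = √(0.8 × 0.5) = 0.632 and p = (0.632 - 0.316) / √(0.75 × 0.6) = 0.471, so p² = 0.222.

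**Step 5: a case with no gain.** With r = 0.5, a = 0.6 and b = 0.3, b - r·a = 0.3 - 0.3 = 0, so p = 0.

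**Step 6: cost if ACT adds nothing.** At SD 6.5 and 30 per arm, going from one covariate to two at p = 0 moves power from 83.37% to 83.34%.

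**The case against.** The strongest reply is that nothing needs correcting. ANCOVA on the outcome's own baseline is standard and valid, and it is the model that the power paragraph assumes. That stands.

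A reader might infer from section 3.0 that the plan itself holds ACT to improve the working-memory measure, and so contradicts itself by leaving ACT out of the primary model. The text does not support this. It raises an open question about a different outcome, the three-test composite, to be tested for the benefit of later trials. It says nothing on whether baseline ACT predicts the week-9 two-test score once the baseline two-test score is known. A reader might also infer that precision is certainly being lost. That needs p above zero, and the documents do not give p.

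The upper ends of the ranges are also favourable. They need a perfectly shared trait, perfect stability and ACT reliability of 0.8 all at once. Lowering the trait correlation to 0.8 cuts the best case from about 18% to 6.4% at r = 0.85. If ACT and the MCCB are given on the same day, shared day-to-day variation could shrink the gain further. The value of r that fits the stated 28 per arm is 0.85, where ACT adds least, and section 9.1.2 describes the MCCB as having high test-retest reliability.

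On the other side, the no-gain case is demanding. A correlation that falls from 0.6 to 0.3 implies, with a single trait, stability of 0.3/0.6 = 0.5 and subscale reliability of 0.5/0.5 = 1.0. That means an error-free baseline, unless the overlap between the tests is purely same-day. Some gain is plausible but cannot be shown from the documents.

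**Conclusion.** The point holds as an optional improvement. The primary model uses one covariate, while a second pre-treatment measure of the same domain is collected and left out. There is no bias, error or internal contradiction in that choice.

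The expected benefit is nil to modest. Over the assumed ranges, residual variance falls by about 0.3% to 18% at r = 0.85 and by about 3.5% to 22% at r = 0.5. At 30 per arm this is a gain of 0.1 to 5.7 points of power in the first case (86.3 - 86.2 and 91.9 - 86.2) and about 1 to 10 points in the second (48.1 - 46.8 and 56.7 - 46.8). All of these figures rest on the assumed reliability, stability and trait correlation, and on independent errors. The case for the change is that its cost is negligible even if the gain is zero.

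**What to change.** Before unblinding, specify in section 8.1 that the primary model is week-9 working memory T-score on treatment arm, baseline working memory T-score and baseline ACT score. Keep the model with baseline working memory T-score alone as a sensitivity analysis. State how a missing baseline ACT score will be handled, so that no patient leaves the primary analysis because of it.

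The cost is a short addition to section 8.1 and one degree of freedom, with no new assessment. The downside is that ACT may add nothing beyond the baseline subscale.

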#### **Secondary Efficacy Endpoint**

- Clinical Global Impression of Change (CGI-C) – this clinician-administered interview is important for demonstrating that improvements in cognition correspond to an overall functional improvement - an FDA requirement for approval of a cognition-enhancing drug for schizophrenia patients.

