#### **9.1.6 Clinical Global Impressions Scale (CGI)**

The Clinical Global Impressions (CGI) Severity and Change Scale will be used for repeated evaluations of global psychopathology. The CGI scale is widely used in schizophrenia research. The CGI-S is a single Likert scale rating severity of psychopathology on a scale of 1 (normal, not ill) to 7 (very severely ill). The CGI-C is a single Likert scale rating change of psychopathology during the trial on a scale of 1

C

(very much improved) to 7 (very much worse). The CGI will be completed at baseline and end of study.

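### CGI-C is already a rating of change, so Section 8.1's change-from-baseline rule and baseline-adjusted ANCOVA do not fit it; the week-9 rating should be compared directly, adjusted for baseline CGI-S

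*Combined protocol and SAP*

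**What the plan says.** Section 9.1.6 describes a two-part instrument. CGI-S rates current severity from 1 to 7. For the other part, "The CGI-C is a single Likert scale rating change of psychopathology during the trial on a scale of 1", the best rating, up to 7, the worst. The timing statement does not separate the two: "The CGI will be completed at baseline and end of study". Appendix 1 likewise has one combined CGI-S/C row, marked on Day 1 and at the final visit.

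CGI-C is the only item under the secondary endpoint heading in Section 3.0, with this reason: "Clinical Global Impression of Change (CGI-C) – this clinician-administered interview is important for demonstrating that improvements in cognition correspond to an overall functional improvement". Section 8.1 places it first in a longer list: "Secondary endpoints will include the Clinical Global Impression of Change (CGI-C); the MCCB composite score", followed by other cognitive and symptom scores.

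On analysis, Section 8.1 states: "All endpoints will be evaluated as 9-weeks change from baseline, except for PANSS, which will be evaluated at both 6 and 9 weeks compared to" (the reference being the baseline value). The model is given as: "The primary analysis will be a univariate ANCOVA adjusting for baseline differences in the dependent measures of interest". The next sentence adds "We would also examine some variables categorically" and names no variables. No separate method for CGI-C appears. CGI-S is collected, but Sections 2.1, 3.0 and 8.1 give it no part in the analysis.

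After setting a responder cutoff of 5 T-score points on the MCCB working memory subscale, Section 3.0 adds: "an analogous approach will be employed for secondary outcomes".

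**The concern.** A change-from-baseline rule suits a state measured twice, such as a T-score or CGI-S. CGI-C compares the patient with the start of the trial inside the rating itself. Subtracting a Day 1 CGI-C, or adjusting for one, has no clear meaning, because on Day 1 there is no trial period to rate. Section 8.1 does write an exception to its rule, but for PANSS only.

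At stake is the endpoint that Section 3.0 relies on to show that a cognitive gain goes with a wider functional gain. With no workable rule on paper, the choice of outcome, covariate and model for CGI-C is left to the analyst, possibly after the data are seen. CGI-S, which does have a true baseline, goes unused.

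**Working it through.** **1. The plan's own figure.** The documents give no effect size, SD or power for CGI-C. The sample size rests on MCCB working memory: difference 5, SD of change 6.5, two-sided alpha 0.05, power 80% (Section 8.1).

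- Normal approximation: n = 2 × (1.960 + 0.842)² × (6.5/5)² = 2 × 7.849 × 1.69 = 26.5, so 27 per group.
- Two-sample t test (noncentral t): power is 79.2% at 27 and 80.7% at 28, so 28 per group, as stated.
- With 20% attrition, 30 becomes 24 per group. Power is 74.2% at 24 and 83.4% at 30, matching the stated 74-83%.

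CGI-C does not enter this calculation, so nothing below changes it.

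**2. Definition against rule.** Let C9 be the week-9 CGI-C and C0 a Day 1 CGI-C. Section 8.1 asks for C9 − C0, modelled with C0 as covariate. Section 9.1.6 makes C9 a change since the start of the trial. The documents do not say what C0 is, which leaves three cases.

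- *C0 not rated (CGI-S only on Day 1).* C9 − C0 can be computed for 0 of 60 patients. C9 itself is intact.
- *C0 = 4 (scale midpoint, no change) for everyone (assumed).* The design matrix of intercept, arm and C0 has rank 2 with 3 columns, so the covariate cannot be estimated. C9 − 4 shifts every rating by a constant. In a simulated data set the arm comparison gave p = 0.0095 for both C9 and C9 − 4.
- *C0 varies (raters enter some pre-study change).* If C0 and C9 are equally variable and uncorrelated, SD(C9 − C0) = √2 × SD = 1.41 × SD.

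**3. Size in the third case.** A simulation assumed 30 per arm, a placebo mean of 3.9, a difference of 0.73, a week-9 SD of 1, and Day 1 ratings centred on 4. Ratings were rounded to whole numbers and kept within 1 to 7. Arms were compared by t test over 4,000 trials per setting. All these values are assumptions.

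- Week-9 rating alone: power about 76%.
- Simple change score: 74%, 65% and 47% for Day 1 SDs of 0.25, 0.5 and 1.0.

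**4. The same case with the ANCOVA.** If C9 − C0 = a + τ·arm + b·C0, then C9 = a + τ·arm + (1 + b)·C0. The arm effect τ is the same whether the outcome is C9 or the change, so the √2 inflation disappears. The cost is one degree of freedom (60 − 3 = 57 instead of 60 − 2 = 58), and the covariate place goes to an uninformative rating. Section 6.0 starts treatment after the baseline assessments, so in each of these cases a Day 1 rating adds noise rather than bias.

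**5. Dropouts.** The intent-to-treat analysis carries the last observation forward. The CGI has only two time points, so a patient without a final rating has at most a Day 1 CGI-C to carry forward. At the plan's 20% attrition that is up to 0.20 × 60 = 12 patients, if none has a final rating.

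**The case against.** The strongest reply is that the week-9 CGI-C already is a nine-week change from baseline. It meets Section 8.1's sentence by construction, and a competent analyst would compare it directly. That stands in part. The data remain usable, and a reader who infers that the endpoint cannot be analysed goes further than the documents allow. The reply does not supply a covariate, though, and the written model calls for a baseline of the dependent measure.

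Three further objections deserve weight.

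- *Scoring CGI-C on Day 1 is inferred from a combined entry.* This is correct. The natural reading is severity at baseline and change at the end, but the plan does not say so. On that reading the literal rule has no CGI-C baseline to use.
- *The ANCOVA sentence is labelled the primary analysis and does not name CGI-C, and Section 8.1 allows some categorical analyses.* Both statements are true. The sentence does refer to dependent measures in the plural. If it is confined to the primary endpoint, CGI-C has no stated model at all.
- *The responder rule is not applied to CGI-C.* A reader might infer that a 5-point cutoff is imposed on a 1-to-7 scale, where the most anyone could improve from a rating of 4 is 4 − 1 = 3 points. The documents do not support this. Section 3.0 speaks of an analogous approach and does not name CGI-C. Section 2.1 gives the secondary label to MCCB scores. Section 8.1 restricts responder analysis to MCCB working memory.

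Section 8.1 also lists CGI-C among several secondary endpoints and describes it as supporting information, so its weight should not be exaggerated.

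**Conclusion.** The point holds as a mismatch between a stated rule and a named secondary endpoint. Section 8.1's change-from-baseline rule and its only model do not fit a measure that Section 9.1.6 defines as change, and the schedule does not separate CGI-S from CGI-C at baseline.

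The consequence is modest. The primary endpoint, the 28 per group and the 74-83% power are unaffected. If Day 1 CGI-C is blank or constant, no information is lost once the week-9 rating is compared directly. Material loss of power needs two assumptions together: Day 1 ratings that vary between patients, and a simple difference without the ANCOVA. The 74% to 47% range also depends on the assumed SDs and effect. Neither an unanalysable endpoint nor a T-score cutoff for CGI-C follows from the documents. What remains is an analysis that should be written down before unblinding.

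**What to change.** - **Section 8.1:** exempt CGI-C from the change-from-baseline rule. Compare the week-9 CGI-C rating directly between arms with baseline CGI-S as covariate, and name the model (for example a proportional-odds model, or a linear model on the score). The choice between these is a matter of judgement that the documents do not settle. Say how a patient without a week-9 rating is handled, since no earlier CGI-C would exist to carry forward.
- **Section 9.1.6 and Appendix 1:** state that CGI-S is rated at baseline and week 9, and CGI-C at week 9 only. Split the combined row accordingly.
- **Section 3.0:** at most, add that the analogous responder approach does not cover CGI-C.

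The cost is wording in these sections, settled before unblinding. No new data are needed, because CGI-S is already collected. Any Day 1 CGI-C already recorded would simply not be used.

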#### **9.1.2 MATRICS Consensus Cognitive Battery (MCCB)**

The MCCB includes 10 tests that assess 7 cognitive domains: speed of processing, attention/vigilance, working memory, verbal learning, visual learning, reasoning and problem solving, and social cognition. The tests will be administered together in one 60-to 90-minute session. For subjects who use nicotine, the MCCB will be performed at least 30 minutes after nicotine intake. Though not strictly required by the protocol, whenever possible, the MCCB should be administered at the same time of day ( $\pm$  1 hour). The MCCB is a hybrid battery comprising multiple independently owned and published tests. Normative data for demographic corrections are derived from a single representative sample to which the tests were administered together as a unit, called "co-norming" [24]. The MCCB's high test-retest reliability makes it a sensitive and accurate measure of cognitive change, and its minimal practice effects ensure that it is appropriate for repeat testing [25]. The MCCB was developed by the National Institute of Mental Health (NIMH) MATRICS initiative. The MATRICS was designed to stimulate the development of psychopharmacological agents to improve cognition in schizophrenia. The selection of tests included in the MCCB involved a broad-based interdisciplinary consensus process that is described in more detail on the MATRICS website ([www.matrics.ucla.edu](http://www.matrics.ucla.edu)). Details of administration are included in the study-specific MCCB manual. The MCCB will be administered at baseline and end of study.

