#### **9.1.3 Positive and Negative Syndrome Scale (PANSS)**

The PANSS is an interview-based measure of the severity of psychopathology in adults with psychotic disorders. The measure is comprised of 30 items and 3 scales: the Positive scale assesses hallucinations, delusions, and related symptoms; the Negative scale assesses emotional withdrawal, lack of motivation, and similar symptoms; and the General Psychopathology scale addresses other symptoms such as anxiety, somatic concern, and disorientation. An anchored Likert scale from 1-7, where values of 2 and above indicate the presence of progressively more severe symptoms, is used to score each item. Individual items are then summed to determine scores for the 3 scales, as well as a total score. A Composite scale score (Positive scale score - Negative scale score) can also be calculated to show the relative valence of positive and negative symptoms. Total time required for the PANSS interview and scoring is approximately 30-40 minutes. PANSS raters will be required to meet specific training and education criteria before they are certified to rate for this study. In addition, raters will receive specific training and education regarding all the following assessments prior to study initiation. The PANSS will be administered at baseline, week 6, and end of study.

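### PANSS is evaluated at weeks 6 and 9 with neither visit named as decisive, and the secondary intent-to-treat analysis carries week 6 forward as week 9

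*Combined protocol and SAP*

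**What the plan says.** Section 9.1.3 fixes the visits: "The PANSS will be administered at baseline, week 6, and end of study". Appendix 1 agrees. For the cognitive battery, section 9.1.2 says "The MCCB will be administered at baseline and end of study". Section 9.1.6 does the same for CGI, and Appendix 1 shows BNSS, fMRI and EEG at those two visits only. PANSS is therefore the only efficacy scale with a mid-trial measurement.

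Section 8.1 takes all endpoints as nine-week change "except for PANSS, which will be evaluated at both 6 and 9 weeks compared to baseline". The only model it names for continuous clinical endpoints is this: "The primary analysis will be a univariate ANCOVA adjusting for baseline differences in the dependent measures of interest". Mixed models appear only in section 8.3, for in-scanner task behaviour and imaging. Section 8.1 applies a 0.05 level throughout and gives no multiplicity rule. In section 2.1, Objective 4 (PANSS positive) and the PANSS part of Objective 3 (PANSS negative) name no visit.

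On populations, section 8.1 begins: "Data will first be analyzed for efficacy on a per-protocol basis". It defines that set as follows: "The per-protocol population will include all subjects who complete all scheduled visits", with further conditions on visit windows, deviations and compliance. It continues: "Data will secondarily be analyzed for efficacy on an intent-to-treat basis, with last observation carried forward (LOCF) for missing values or dropouts".

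**The concern.** There are two separate problems.

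- **Choice of visit.** A univariate ANCOVA evaluated at two visits amounts to two fits per scale. The text does not say this outright, but it offers no other method. With each fit at 0.05 and no visit named as decisive, a symptom benefit could be reported from whichever week is significant.
- **Carry-forward.** In the intent-to-treat analysis, a patient with a week-6 score and no week-9 score enters week 9 with the week-6 value. This assumes no change over the last three weeks and treats the filled-in value as observed.

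At stake are the conclusions on positive and negative symptoms, which section 3.0 states as a hypothesis of the trial.

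**Working it through.** **The plan's own figures.** The documents give no power or error rate for PANSS. The figures in section 8.1 are for MCCB working memory: a 5-point difference, SD of change 6.5, two-sided 0.05. A two-sample t calculation gives 80.7% power at 28 per group, 83.4% at 30, and 74.2% at 24 (30 × 0.8). The stated 28 per group and 74–83% therefore reproduce, but they do not bear on PANSS.

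**Error over two visits.** The chance that at least one visit is falsely significant is 1 − P(|Z6| < 1.96 and |Z9| < 1.96), where Z6 and Z9 are bivariate normal with correlation ρ. The documents give no PANSS correlation. The power paragraph of section 8.1 assumes 0.5 with compound symmetry for the MCCB. Borrowed here, that gives a correlation between the two baseline-adjusted visits of (0.5 − 0.5²)/(1 − 0.5²) = 1/3.

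| ρ | Either-visit error |
|---|---|
| 0 | 9.75% (= 1 − 0.95²) |
| 1/3 | 9.5% |
| 0.5 | 9.1% |
| 0.7 | 8.3% |
| 0.9 | 7.0% |

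A simulation with 30 per arm (4,000 runs per setting; correlation 0.5 or 0.7; dropout 0, 6.7% or 20%) gave 8.9% to 9.6% for either visit. A single week-9 test stayed near 5% by either method: 4.6% to 5.5% for the LOCF ANCOVA and 4.2% to 5.1% for a likelihood estimate that stands in for a repeated-measures model.

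**Bias from carry-forward.** Let m be the fraction with a week-6 but no week-9 score, equal in both arms, and let k be the week-6 effect divided by the week-9 effect. The LOCF effect at week 9 is then (1 − m) + mk times the true one, so the attenuation is m(1 − k). Section 8.1 allows attrition up to 20%, which is 12 of 60 patients. The timing of dropout and k are assumptions.

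- All 20% lost after week 6, k = 0.5: 0.20 × 0.5 = 10%.
- A third of losses in that window (m = 0.20/3 = 0.067, about 4 patients), k = 0.5: 0.067 × 0.5 = 3.3%.
- Flat effect, k = 1: 0.

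The simulation agrees. With true effects of 0.4 SD at week 6 and 0.6 SD at week 9, LOCF estimated 0.56 at 20% dropout (formula: 0.6 × (1 − 0.2 × 1/3) = 0.56) and 0.59 at 6.7%. The likelihood estimate was 0.60 in both.

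**Power.** At correlation 0.5, 20% dropout and effects of 0.4 and 0.6 SD, simulated power was 0.68 for LOCF and 0.64 for the likelihood estimate. With 0.6 SD at both visits it was 0.75 and 0.64.

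**The case against.** The strongest case on the other side is that little depends on this and that a mixed model is the wrong remedy for half of it. Most of that stands.

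- **Carry-forward is not the lead PANSS analysis.** A reader might infer that week 6 generally stands in for week 9. The documents do not support that. The per-protocol analysis comes first and requires all scheduled visits, so no dropout is carried forward there. LOCF belongs to the secondary analysis and puts week 6 into week 9 only for patients who have the first score and lack the second.
- **A repeated-measures model does not cure double testing.** It still yields a contrast at each visit. Naming one visit is what brings the error back to 5%, and the planned ANCOVA would do equally well for that.
- **Nor does it gain power over LOCF.** One might expect recovered information. Against completers the variance ratio is 1 − mρ². At m = 0.2 that is a reduction of 5% to 13% for correlations of 0.5 to 0.8, and about 2% at 1/3. The method being replaced is LOCF, however, and against LOCF simulated power was lower.
- **The 10% figure is a worst case.** It places every loss after week 6 and assumes a half-size effect there. The documents give no PANSS trajectory. The only one they give (section 1.1.2, cognition in another population) is mixed: the battery effect rises from 0.74 to 0.91, while Digit Span falls from 0.61 to 0.30.
- **Consequence is limited.** Section 3.0 lists positive and negative symptoms as tertiary or exploratory, and section 8.1 lists them as secondary. The MCCB has a single post-baseline visit, so nothing here reaches the primary conclusion.

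What the objection leaves in place is that the plan allows a choice of visit and fills in week-9 scores by a rule that can bias the estimate.

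**Conclusion.** The point holds as a low-cost improvement. The open choice of visit raises the per-scale false-positive chance from 5% to about 7% to 9.5%, for test correlations from 0.9 down to 1/3. In the secondary intent-to-treat analysis, LOCF shrinks the week-9 effect if the effect grows between visits: by about 10% in the worst case considered, about 3% with a third of losses in the window, and near zero if the effect is flat. The 10% depends on the assumed half-size week-6 effect and is not a mathematical bound. PANSS correlations, effect trajectory and dropout timing are all assumptions. The documents do not support a claim that the lead PANSS analysis or the primary endpoint is biased.

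**What to change.** 1. In section 8.1, name the week-9 arm contrast as the PANSS result for Objective 4 and the PANSS part of Objective 3, with week 6 supportive. This applies to the per-protocol and intent-to-treat analyses alike and is enough to remove the double testing within each scale.
2. For the intent-to-treat analysis of PANSS positive and negative, replace the LOCF ANCOVA with one repeated-measures model of change at weeks 6 and 9. Terms: arm, visit, arm-by-visit, baseline and baseline-by-visit, with unstructured covariance. Keep LOCF as a sensitivity analysis only.
3. Report by arm the number of treated patients with no post-baseline PANSS.

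The cost is a few sentences and standard code, with no new data, and it should be settled before the blind is broken. There are two downsides. The model relies on missing-at-random dropout, which cannot be verified from the data. Treated patients who leave before any post-baseline PANSS contribute nothing to it, although the plan's full analysis set excludes only those who received no study compound; hence the count in item 3.
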